13.7. Key Elements of Analysis Plan

Data will be listed and summarized according to the GSK reporting standards, where applicable. Complete details will be documented in the RAP. Any deviations from, or

additions to, the original analysis plan described in this protocol will be documented in the RAP and final study report.

As it is anticipated that accrual will be spread thinly across centers and summaries of data by center would be unlikely to be informative, data from all participating centers will be pooled prior to analysis.

All data up to the time of study completion/withdrawal from study will be included in the analysis, regardless of duration of treatment.

As the duration of treatment for a given subject will depend on efficacy and tolerability, the duration of follow-up will vary between subjects. Consequently there will be no imputation for missing data.

Demographic and baseline characteristics will be summarized.

13.7.1. Anti-Cancer Activity Analyses

The Efficacy Population will be used for anti-cancer activity analyses. Since this is a Phase I study, anti-cancer activity will be evaluated based on clinical evidence and response criteria. Where appropriate, the lesion data will be listed for each subject. The percent change from baseline will be calculated for each subject and listed, along with their ORR, CR, PR, SD and PD according to standard RECIST 1.1 (See [Appendix 5](#)). mRECIST and irRc will be calculated and listed as applicable. Response data will be summarized by cohort or group. If data warrant, the response data will be summarized by dose level. Response-evaluable subjects are defined as subjects with a pre-dose and at least 1 post-dose disease assessment. Correlation analysis may be conducted to explore any relationship between the subject's tumor type specific markers and tumor response based on RECIST, version [1.1], mRECIST and irRc. Other measures of clinical benefit specific to the groups in Part 2 will be summarized by group as appropriate.

Full details will be specified in the RAP.

13.7.2. Safety Analyses

The All Treated Population will be used for the analysis of safety data. All serially collected safety endpoints (e.g., laboratory tests, vital signs, ECGs) will be summarized according to the scheduled, nominal visit at which they were collected and across all on-treatment time points using a "worst-case" analysis.

DLTs will be listed for each subject and summarized according to GSK IDSL standards. All other relevant safety data will be listed and summarized according to the GSK IDSL standards as well. Complete details of the safety analyses will be provided in the RAP.

13.7.2.1. Extent of Exposure

Extent of exposure of GSK2849330 will depend on tolerability of the subjects to the doses administered and the course of their disease.

The number of subjects administered study treatment will be summarized according to the duration of therapy.

13.7.2.2. Adverse Events

AEs will be coded using the standard MedDRA and grouped by system organ class. AEs will be graded by the investigator according to the NCI-CTCAE, (version 4.0) [NCI, 2009]. Summaries of the number of toxicity grades for both laboratory and non-laboratory data will be presented.

Events will be summarized by frequency and proportion of total subjects, by system organ class and preferred term. Separate summaries will be given for all AEs, treatment-related AEs, SAEs and AEs leading to discontinuation of study treatment. AEs, if listed in the NCI-CTCAE (version 4.0) [NCI, 2009] will be summarized by the maximum grade. Otherwise, the AEs will be summarized by maximum intensity.

The incidence of deaths and the primary cause of death will be summarized.

DLTs will be listed for each subject and summarized by dose cohort according to IDSL standards.

13.7.2.3. Clinical Laboratory Evaluations

Clinical laboratory evaluations will be performed on the days specified in the Time and Events Tables Section 7.1.

Hematology and clinical chemistry data will be summarized using frequencies and proportions according to NCI-CTCAE (version 4.0) [NCI, 2009]. Laboratory test results outside the reference ranges that do not have associated NCI-CTCAE criteria will be summarized at each scheduled assessment. Results will be flagged using toxicity grades, if available, or as normal or abnormal (high or low) with reference to standard reference ranges. Further details will be provided in the RAP.

13.7.2.4. Other Safety Measures

Data for vital signs, ECGs, and ECHOs will be summarized based on predetermined criteria identified to be of potential clinical importance (PCI). Vital signs will be listed for each subjects at all measured time points. A descriptive summary including change from baseline pre-dose will also be presented. Individual profiles of BP will be plotted by time. Further details will be provided in the RAP.

13.7.3. Pharmacokinetic Analyses

13.7.3.1. Pharmacokinetic Parameters

PK analysis will be the responsibility of the Clinical Pharmacology Modeling and Simulation (CPMS) Department, GSK.

PK analysis of drug concentration-time data will be conducted by non-compartmental methods and exploratory compartmental methods under the direction of CPMS, Quantitative Sciences, GSK. The following PK parameters will be determined if data permit:

- C_{max}
- t_{max}
- area under the plasma concentration-time curve (AUC(0-t), AUC(0-τ) (repeat dosing) and/or area under the concentration-time curve from time zero (pre-dose) extrapolated to infinite time [AUC(0-∞)] (single dose)
- apparent terminal phase elimination rate constant (λ_z) (single dose)
- apparent terminal phase half-life (t_{1/2}) (single dose)
- apparent MRT
- population pharmacokinetic parameters including CL, Q, V, V_m and K_m

13.7.3.2. Statistical Analysis of Pharmacokinetic Data

Statistical analyses of the non-compartmental PK parameters data will be the responsibility of Oncology, Clinical Statistics, GSK. Statistical analysis of the exploratory compartmental PK parameters data will be the responsibility of CPMS, Quantitative Sciences, GSK. Plasma GSK2849330 concentration-time data from dose escalation will be analyzed by non-compartmental methods with WinNonlin [Version number 5.2].

From the plasma concentration-time data, the following PK parameters will be determined, as data permit: C_{max}, t_{max}, AUC(0-t) and AUC(0-∞), apparent terminal phase half-life (t_{1/2}), and MRT. Trough concentration (C_τ) samples collected on the specified days will be used to assess attainment of steady state.

Plasma concentration-time data will be listed by dose and summarized using descriptive statistics (n, mean, standard deviation SD, median, minimum and maximum) by planned relative assessment time. Mean and/or median values will be plotted over time. Individual plasma and urinary (if available) PK parameters values as well as descriptive summary (mean, SD, median, minimum, maximum, geometric mean, and the standard deviation, 95% confidence interval (CI) of log-transformed parameters (if applicable) by dose cohort or group will be reported.

C_{max} and AUC (AUC(0-∞), and AUC(0-τ)) will be plotted as a function of the dose administered.

Further exploratory statistical analysis of any or all the pharmacokinetic endpoints may be performed as appropriate including dose proportionality.

PK data will be presented in graphical and/or tabular form and will be summarized descriptively.

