The predicted half-life for GSK2849330 after the first dose is ~7 days and increases to ~10 to 14 days after repeated dosing and is expected to support dosing frequency from weekly to every three weeks. However, at lower doses, including the proposed starting dose, the contribution of target mediated clearance may yield a half-life somewhat shorter than projected for higher dose levels. With this consideration, the initial dosing frequency for the first subject will be once-weekly. PK data will be evaluated from the first week of dosing for the first subject, so that adjustments in the dosing interval can be made if appropriate (see the Time and Events Tables Section 7.1 and Section 7.4 for the specific PK assessment schedule for the first subject).

If the half-life appears to be generally in line with expectations, the dosing interval for higher dose cohorts is anticipated to be every week or every 2 weeks. A general guideline is shown in Table 4. Additional schedules may be explored based on safety, tolerability, PK and PD.

Table 4 Dosing Interval Guidance

Observed half-life	Likely dose interval*
<3 days	Once-weekly
4-8 days	Every week or every 2weeks
> 9 days	Every 3 weeks

*Final selection of dose interval for cohorts will take into consideration the half-life together with safety, tolerability, PK and available PD data.

It is recognized that increasing the dose can allow for extension of the dosing interval with equivalent safety and efficacy, assuming that 1) toxicity is not limited by C_{max} and 2) efficacy is related to overall exposure (AUC) or time above a given concentration. Both assumptions appear reasonable for GSK2849330 based on 1) preclinical safety data and 2) preclinical efficacy data and knowledge of the mechanism of action. Based on human PK predictions from cynomolgus monkey data, a dose of 2.9 mg/kg every 3 weeks IV may provide the same exposure in 3 weeks as 3 doses of 1.2mg/kg every week IV at steady state. Using these principles, it is anticipated that the dosing schedule may be lengthened as appropriate based on accrual of PK and/or PD information.

Additional context for the proposed doses are provided in the following sections.

Human Pharmacokinetic Extrapolation

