7.4. Pharmacokinetics

For subjects enrolled in Part 1, dose escalation Cohorts 1-4, blood samples for analysis of GSK2849330 concentrations will be collected on Day 1: pre-dose and at 1 hour and 6 hours after the end of infusion and at Day 8, Day 15, and Day 29 after the first dose of GSK2849330. If a subject's duration of infusion is 3 hours or longer, the 6-hour time point is optional. On days of dosing, the sample will be drawn pre-dose. Additionally the first subject in Cohort 1 will have PK samples taken at 24 hour (Day 2) and 72 hour (Day 4) after the end of infusion.

For cohorts enrolled under Amendment 1 of this protocol, more frequent PK samples will be collected on Day 1: pre-dose and at 1 hour, 6 hours and 24 hours after the end of infusion;. Pre-dose samples will also be collected on Day 4, Day 8, and weekly through Day 57 with additional 1 hour post-dose samples collected on Days 29 and 57. Pre-dose samples will also be collected on Day 71, Day 85, and every 12 weeks thereafter.

For all subjects in the Part 1 PK/PD cohorts, blood samples for analysis of GSK2849330 concentrations will be collected on scheduled dosing Days 1: pre-dose and at 1 hour, 6 hours and 24 hours after the end of infusion. Pre-dose samples will also be collected on Day 4, Day 8, and weekly through Day 57 with additional 1 hour post-dose samples collected on Days 29 and 57. Pre-dose samples will also be collected on Day 71, Day 85 and every 12 weeks thereafter.

For the molecularly defined tumor histology groups in Part 2, blood samples for analysis of GSK2849330 concentrations will be collected on Day 1: pre-dose and at 1 hour after the end of infusion; and pre-dose on Day 15, Day 29, Day 43, Day 57, Day 71, Day 85, and every 12 weeks thereafter.

For all subjects (Part 1 and Part 2), if treatment continues beyond 1 year, samples will be collected every 24 weeks. An additional PK sample will also be taken at the Follow-up visit (28 days after the last dose of study treatment), and/or the Post study visit (45 days or 5 half-lives [whichever is longer] after the last dose of study treatment). Unless stated otherwise, on days of dosing PK samples will be drawn pre-dose.

See the Time and Events Tables Section 7.1 and the SPM for additional details on the PK sample timing.

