### 13.2. Deriving and Summarizing Pharmacokinetic Parameters

All PK parameter displays will be based on PK parameter population.

As data permit, the following pharmacokinetic parameters will be determined from the plasma concentration-time data for GSK2849330. The pharmacokinetic parameters will be calculated by standard non-compartmental analysis according to current working practices and using WinNonlin Professional Version 6.3 or higher. All calculations of non-compartmental parameters will be based on actual sampling times.

- 1. The first occurrence of the maximum observed plasma concentration determined directly from the raw concentration-time data (Cmax).
- 2. The time at which Cmax is observed will be determined directly from the raw concentration-time data (tmax).
- 3. The apparent terminal elimination half-life  $(t_{1/2})$  obtained as the ratio of  $\ln 2/\lambda z$ , where  $\lambda z$  is the terminal phase rate constant estimated by linear regression analysis of the log transformed concentration-time data
- 4. The time to reach the last quantifiable concentration (tlast)
- 5. The area under the plasma concentration-time curve to the last quantifiable concentration (AUC(0-t)) determined using the linear trapezoidal rule for increasing concentrations and the logarithmic trapezoidal rule for decreasing concentrations.
- 6. The AUC to a fixed nominal time (AUC(0-168)) will be calculated using the linear trapezoidal rule for increasing concentrations and the logarithmic trapezoidal rule for decreasing concentrations.
- 7. The AUC over the dosing interval (AUC( $0-\tau$ )), where  $\tau$  is the dosing interval, will be calculated using the linear trapezoidal rule for increasing concentrations and the logarithmic trapezoidal rule for decreasing concentrations.
- 8. The AUC extrapolated to infinity (AUC(0- $\infty$ )) will be calculated, where data permit, as the sum of AUC(0-t) and Ct/ $\lambda z$ , where Ct is the observed [insert matrix] concentration of the last quantifiable time-point and  $\lambda z$  is the terminal phase rate constant obtained from the log-linear regression analysis.
- 9. The percentage of AUC( $0-\infty$ ) obtained by extrapolation (%AUC $\infty$ ex) will be calculated as the ratio of [AUC( $0-\infty$ ) minus AUC(0-t)] to AUC( $0-\infty$ ) X 100.

- 10. C $\tau$ : pre-dose (trough) concentration at the end of the dosing interval on the specified days (Only for Days 8, 15 and 22 where available).

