# 13.3. Statistical Analyses of Pharmacokinetic Data

Statistical analyses of pharmacokinetic parameters will be responsibility of Oncology, Clinical Statistics, GSK. Statistical analysis of the exploratory compartmental PK parameters data will be the responsibility of CPMS, Quantitative Sciences, GSK.

PK data will be presented in graphical and/or tabular form and will be summarized descriptively.

For all statistical analyses, AUC( $0-\infty$ ), AUC(0-t), AUC( $0-\tau$ )), AUC(0-168), t1/2, and Cmax will be separately analysed after loge-transformation.

Individual plasma PK parameters values as well as descriptive summary (mean, SD, median, minimum, maximum, geometric mean, and the standard deviation, 95% confidence interval (CI) of log-transformed parameters (if applicable) by dose group will be reported.

Pre-dose trough concentration (C  $\tau$ ) samples obtained immediately before the morning dose on Days 8, 15, and 29 will be presented in a listing and will be summarized descriptively by dose.

Box plot figures will be generated based on dose normalized data for Cmax and AUC(0- $\infty$ ), AUC(0-168), and AUC(0- $\tau$ )) as a function of the dose administered.

Individual and Box Plot of Plasma GSK2636771 Pre-Dose Concentration Data on Day 8, 15 and 29 by Dose Cohort in Part 1 will be provided.

Statistical analysis of Cmax and AUC may be performed as appropriate dose proportionality.

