# 19.1.5. Pharmacokinetic Figures and Tables

# **Figures**

Figure No.	Population	IDSL No. / Example Shell	Title	Programming Notes	Deliverable Priority
13.1	PK parameter	PK16a, pkcf1p	Individual Plasma GSK2849330 Concentration-Time Plots by Dose Cohort in Part 1 (Linear and Semi-log)		SAC
13.2	PK parameter	РК17, РКСF2	Mean (± SD) GSK2849330 Plasma Concentration-Time Plots by Dose Cohort in Part 1 (Linear and Semi-log)		SAC
13.3	PK parameter	PK18, pkcf3	Median GSK2849330 Plasma Concentration-Time Plots by Dose in Part 1 (Linear and Semi-log)		SAC
13.4	PK parameter		Individual and Box Plot of Dose-Normalized Plasma GSK2636771 PK Parameters by Dose Cohort in Part 1	For Cmax, AUC(0-∞), AUC(0-168), and AUC(0-т) arenv/arprod/gsk263 6771/p3b115717/sac /drivers/f_pkp_box_s ingle.sas	SAC
13.5	PK parameter		Individual and Box Plot of Plasma GSK2636771 Pre-Dose Concentration Data on Day 8, 15 and 29 by Dose Cohort in Part 1	arenv/arprod/gsk263 6771/p3b115717/sac /drivers/f_pkc_box_p re.sas	SAC

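### The SAP's trough analyses stop at Day 22 or Day 29, while troughs are expected still to be rising, so on their own they cannot show the steady state that the protocol wants assessed

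*Protocol*

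**What the plan says.** Protocol 13.7.3.2 gives the trough samples a stated purpose: they "samples collected on the specified days will be used to assess attainment of steady state".

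The SAP then fixes the days in three places:

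- 13.2, item 10 derives the trough parameter "Only for Days 8, 15 and 22 where available".
- 13.3 says that pre-dose "samples obtained immediately before the morning dose on Days 8, 15, and 29 will be presented in a listing", with a descriptive summary by dose.
- Figure 13.5 in 19.1.5 plots "Pre-Dose Concentration Data on Day 8, 15 and 29 by Dose Cohort in Part 1".

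I found no mention of steady state in the SAP and no rule for judging it.

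The protocol collects later pre-dose samples. Section 7.4 has the Amendment 1 and PK/PD cohorts sampled weekly through Day 57, and then "Pre-dose samples will also be collected on Day 71, Day 85, and every 12 weeks thereafter". For Part 2 it asks for samples on Day 1 "and pre-dose on Day 15, Day 29, Day 43, Day 57, Day 71, Day 85, and every 12 weeks thereafter". The original dose-escalation Cohorts 1-4 have Days 8, 15 and 29. Table 7, footnote 12 then adds a sample every 12 weeks from the first dose, the first of which falls on about Day 85.

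On kinetics, Protocol 3.6.3 states: "The predicted half-life for GSK2849330 after the first dose is ~7 days and increases to ~10 to 14 days after repeated dosing". The same section gives the preliminary population model (Table 6) and a catabolic half-life of 172 hours.

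**The concern.** A trough analysis shows attainment of steady state only if its last few days lie on the flat part of the accumulation curve. With a repeat-dose half-life of 10 to 14 days, Day 29 is only two to three half-lives after the first dose. The two SAP day sets also disagree on whether the last day is Day 22 or Day 29. Under every-2-week dosing, Days 8 and 22 are mid-interval and not troughs at all.

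Characterising PK is a secondary objective in both parts (Protocol 2.1 and 2.2), and Protocol 3.6.3 justifies the 30 mg/kg weekly cohort by reference to an accumulated steady-state trough. If a reader took the last displayed trough as the steady-state value, that value would be understated.

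**Working it through.** **Inputs.** Table 6: CL 11.4 mL/h (RSE 39.1%), V1 2830 mL, Q 79.0 mL/h, V2 3420 mL, VM 198 µg/h, KM 0.513 µg/mL, fitted to five subjects (1 + 2 + 2). Half-lives from 3.6.3: about 7 days after the first dose, and 10-14 days after repeated dosing. Body weight is an assumption: 60 kg (the protocol's scaling weight), also run at 70 and 80 kg.

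**The protocol's own figure.** ln 2 × V1/CL = 0.6931 × 2830/11.4 = 172 h (7.2 days), which reproduces the stated value. This uses the central volume only. With k10 = 11.4/2830, k12 = 79/2830 and k21 = 79/3420, the slow rate constant of the linear two-compartment model gives a terminal half-life of 397 h, or 16.5 days. That is the half-life that governs accumulation under Table 6.

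**Share of the steady-state trough on Day D.** For a single half-life the share is 1 − 2^(−(D−1)/t½), whatever the dose or interval. On Day 29, for example, 1 − 2^(−28/14) = 0.75 and 1 − 2^(−28/7) = 0.94. For Table 6, the full model (peripheral saturable elimination, 1-hour infusion) was solved numerically for the Part 1 regimens at 60, 70 and 80 kg.

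| Basis | Day 15 | Day 29 | Rise, Day 15 to 29 | Day 57 | Day 85 | Rise, Day 57 to 85 |
|---|---|---|---|---|---|---|
| 7 days | 75% | 94% | 25% | 99.6% | >99.9% | <1% |
| 10 days | 62% | 86% | 38% | 98% | 99.7% | 2% |
| 14 days | 50% | 75% | 50% | 94% | 98% | 5% |
| Table 6 | 44-48% | 69-71% | 50-56% | 90-91% | 97% | about 7% |

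The Table 6 rises come from 0.712/0.475 = 1.50 (1.4 mg/kg weekly, 60 kg) and 0.691/0.444 = 1.56 (30 mg/kg weekly).

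**The Day 22 set.** Only weekly regimens have a true Day 22 trough. The rise from Day 15 to Day 22 runs from 17% (7 days: 0.875/0.75) to 32% (Table 6, 30 mg/kg weekly: 0.586/0.444).

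**Day 8 under every-2-week dosing.** For 30 mg/kg every 2 weeks at 60 kg, the expected values on Days 8, 15 and 29 are 62%, 44% and 69% of the steady-state trough. The sequence falls and then rises because Day 8 is mid-interval.

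**Size if Day 29 were read as steady state.** The understatement is 6% at 7 days, 14-25% at 10-14 days, and 29-31% under Table 6. For 30 mg/kg weekly at 70 kg, the Table 6 steady-state trough is about 885 µg/mL and Day 29 is 0.691 × 885 = 612 µg/mL.

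**Sensitivity.** Moving CL by one RSE in the linear two-compartment model puts Day 29 anywhere from 52% to 80%.

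**The case against.** The strongest reply is that the later samples are not lost. SAP 13.1 lists plasma concentrations and summarises them by dose group and nominal time. Listing 13.3 and Table 13.1 have no Day 29 cut-off, Figures 13.1-13.3 plot Part 1 concentrations over time, and population PK may use everything. This stands. A reader might infer that the steady-state question cannot be answered at all, or that the Day 43-85 samples go unused; the documents do not support either. What is missing is a trough analysis on those days. The general displays do not wholly replace it: they mix all nominal times, and the planned concentration-time figures are for Part 1. Summaries use the PK Parameter population, so a sparsely sampled Part 2 subject without derived parameters could appear only in a listing.

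The second reply is that the figure of about 70% is fragile. That also stands. It is a Day 29 value from a preliminary five-subject fit, and it is not a property of every regimen throughout Days 8-29. The 7-day half-life gives 94%. But 3.6.3 applies that half-life to the first dose, and even then the trough is still rising by 25% between Days 15 and 29.

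Third, later troughs bring their own problem. Protocol 3.5 allows intra-subject dose escalation after the first 28 days, and 3.9.4 lets 30 mg/kg weekly subjects move to every 2 weeks for toxicity. SAP 8.1 reports all data under the starting regimen. Pooling late troughs without a rule could mix doses and intervals. This stands, and the fix has to deal with it.

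Fourth, Days 8, 15 and 29 are the sampling days that the original Cohorts 1-4 had, and Days 43-71 were not scheduled for them. SAP 7.1 shows 1.4 mg/kg weekly and 3 mg/kg every 2 weeks as dose-escalation groups only, so those troughs may not exist there. That limits what can be shown for these groups, but it does not explain stopping at Day 29 for the others.

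Finally, no passage plans to report Day 29 as steady state, and dose decisions rest on ongoing data reviews (SAP 4.1). The understatement is therefore a risk of misreading, not a planned error.

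**Conclusion.** The point holds in a limited form. The protocol assigns troughs to the assessment of steady state. The SAP's trough analyses end at Day 22 or Day 29, the two day sets disagree, and on every half-life the protocol states, and under Table 6, the trough is still climbing by 25-56% from Day 15 to Day 29. Those days alone cannot show a plateau. The late days are much better placed: from Day 57 to Day 85 the expected rise is at most about 7%.

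The Day 29 share should be quoted as a range: 69-71% under Table 6, 75-86% at 10-14 days, and 94% at 7 days. These figures rest on point estimates, full adherence to one regimen, and assumed weights of 60-80 kg for Table 6; the CL estimate is imprecise. The defect is in the trough analysis and its day rule, not in data collection.

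**What to change.** Reconcile SAP 13.2 item 10, SAP 13.3 and Figure 13.5 to one day set per regimen, defined as pre-dose samples on actual dosing days through Day 85 where scheduled. This removes Days 8, 22, 36 and 50 for every-2-week regimens. Include the Part 2 groups in the listing, summary and plot, and show n at each day. Include only subjects still on their initial dose and interval, censoring at any change in either. State how steady state will be judged, and base that statement on the Day 57-85 troughs where available. For the original Cohorts 1-4, say that the only late trough is the 12-weekly sample at about Day 85. While editing, correct the compound name in 13.3 and in the Figure 13.5 title, which refer to GSK2636771.

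No new samples are needed. The cost is SAP text plus programming of the censoring rule from the exposure data. Fewer subjects will contribute at later days, and the early stopping noted in SAP Section 11 may reduce them further. There will be no Day 43-71 values from subjects on the original escalation schedule.
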